6.1.4 Confidentiality and privacy

Participant confidentiality and privacy is strictly held in trust by the participating investigators, their staff, and the Sponsor and their contracted vendors. This confidentiality is extended to cover testing of biological samples and genetic tests in addition to the clinical information relating to participants. Therefore, the study protocol, documentation, data, and all other information generated will be held in strict confidence. No information concerning the study or the data will be released to any unauthorized third party without prior written approval of the Sponsor.

All research activities will be conducted in as private a setting as possible.

The study monitor, other authorized representatives of the sponsor, representatives of the ECs, regulatory agencies or pharmaceutical company supplying the IMP may inspect all documents and records required to be maintained by the investigator, including but not limited to, medical records (office, clinic, or hospital) and pharmacy records for the participants in this study. The clinical study site will permit access to such records.

The study participant's contact information will be securely stored at each clinical site for internal use during the study. At the end of the study, all records will continue to be kept in a secure location for as long a period as dictated by the ECs, regulatory agencies, or Sponsor requirements.

Study participant research data, which is for purposes of statistical analysis and scientific reporting, will be transmitted to and stored at **stored**. This will not include the participant's contact or identifying information. Rather, individual participants and their research data will be identified by a unique study identification number. The study data entry and study management systems used by clinical sites and by **store** research staff will be secured and password protected. At the end of the study, all de-identified study databases will be archived at the Sponsor.

6.1.5 Future Use of Stored Samples

Available biological samples (serum, cells and CSF) will be stored for potential exploratory assessments, e.g. potential biomarkers (CSF neurogranin, CSF VILIP-1, plasma NFL, A β 1-42 and A β 1-40), antibodies against vaccine components, functional capacity of vaccine-induced antibodies, binding of vaccine-induced antibodies to human paired filament tau, anti Tau B cell response, T cell activation in CSF, B cell activation in blood. Future use will be limited to research related to the study vaccines and/or Alzheimer's disease.

With the participant's approval and as approved by ECs, de-identified leftover blood and CSF samples will be stored at a Biosample Repository for up to 10 years after the end of the study (i.e. last subject completing the last follow-up visit). Genetic analyses will not be conducted with the leftover samples. Permission to transmit and store biological samples to long-term biosample repository will be included in the informed consent.

An individual participant can choose to withdraw consent to have biological specimens stored for future research anytime during the storage period.

6.2 Indemnification

The sponsor's indemnification of the investigator and institution during the conduct of this study is addressed in a letter of indemnification provided as a separate document. Other indemnification or insurance will be provided as necessary under EU and local regulations.

6.3 Discontinuation of the Study by the Sponsor

Should it prove necessary to discontinue the study permanently prior to completion (e.g. for compromised safety), subjects will be examined as per the final visit and appropriate early study completion CRFs completed.

In case it is decided to terminate the study prematurely, the sponsor will immediately notify investigators, relevant authorities and additional contacts. Investigators will promptly notify their relevant Ethics Committees and the study participants. The study products and materials will be returned.

In the Netherlands, based on Article 3 of the Revised CCMO Directive on the Assessment of Clinical Trial Agreements dated 1 November 2011, premature termination is only possible:

- a. if the judgement of the competent medical research ethics committee that has assessed the study is irrevocably revoked;
- b. if a reasonable case can be made for terminating the study in the interests of the health of the research subjects;
- c. if it transpires that continuation of the study cannot serve any scientific purpose, and this is confirmed by the medical research ethics committee that has issued a positive decision on the study;
- d. if one of the parties or the funder has been declared insolvent or a bankruptcy/windingup petition has been filed in respect of one of the parties or the financier, or one of the parties or the financier is dissolved as a legal entity;
- e. if the principal investigator is no longer capable of performing the tasks of the principal investigator, and no replacement agreeable to both parties can be found;
- f. if one of the two parties fails to comply with the obligations arising from the agreement and, provided compliance is not permanently impossible, this compliance has not taken place within thirty days of the defaulting party receiving a written request to comply, unless failure to comply is not in reasonable proportion to the premature termination of the study;
- g. if circumstances beyond the control of the sponsor, investigator or funder make it unreasonable to require the study's continuation.

6.4 Study Monitoring and Auditing

This study will be monitored for quality assurance at all stages of its development and conduct by the clinical research personnel employed by the sponsor or its representative. Monitoring will include personal visits and telephone communication to assure that the investigation is conducted according to the protocol, standard operating procedures, Guidelines of Good Clinical Practice, and applicable regulatory requirements. Quality control procedures will be applied to each stage of data handling to ensure that all data are reliable and have been processed correctly. On-site review of eCRFs will include a review of forms for completeness and clarity, and consistency with source documents available for each subject. A variety of original documents, data and records will be considered as source documents in this trial. The eCRF itself is not to be used as a source document under any circumstances.

Medical advisors and CRAs or assistants may request to witness subject evaluations occurring as part of this protocol. The investigator and appropriate personnel will be periodically requested to attend meetings organized by the sponsor to assure acceptable protocol execution. The study may be subject to audit by the sponsor or by regulatory authorities. If such an audit occurs, the investigator must agree to allow access to required subject records. By signing this protocol, the investigator grants permission to personnel from the sponsor, its representatives, and appropriate regulatory authorities, for on-site monitoring of all appropriate study documentation,

as well as on-site review of the procedures employed in eCRF generation, where clinically appropriate.

6.5 Retention of Records

The investigational sites will maintain all trial documentation and take measures to prevent accidental or premature destruction of these documents.

The investigator agrees to keep records, including the identity of all participating subjects, all original signed Informed Consent Forms, a copy of all eCRFs, and detailed records of drug disposition. These should be kept in an Investigator's File that should be set-up by the Sponsor and kept regularly updated by the Investigator during the study.

To comply with international regulations, the records should be retained by the Investigator following the duration of the most stringent authority. The investigational sites must notify the sponsor before destroying any data or records.

6.6 Use of Study Findings

By signing the study protocol, the investigator agrees to the use of results of the study for the purposes of national and international registration. If necessary, the authorities will be notified of the investigator's name, address, qualification, and extent of involvement. Reports covering clinical and biometric aspects of the study will be prepared by the sponsor or its representative.

6.7 Publications

As a multicenter trial, the sponsor intends to publish clinical data from all centers participating in the investigation. A publication committee selected by the sponsor will submit draft manuscripts to all participating investigators for their comments. In conformity with the Uniform Requirements for Manuscripts Submitted to Biomedical Journals published by the International Committee of Medical Journal Editors, investigators whose contribution consists solely in the collection of data will not be named individually as authors. Rather, those investigators will receive a collective authorship and will be identified in a note.

Individual investigators and/or their associates subsequently may publish additional finding of the study in scientific journals or present them at scientific meetings, provided that the sponsor is given ample opportunity to review any proposed abstract, manuscript, or slide presentation before its submission. This review is required to ensure that the sponsor is aware of all written and oral presentations of the data and does not imply any editorial review or restriction of the contents of the presentation or use.

8. APPENDICES

Appendix 1 NIA/AA Criteria for probable AD Dementia (McKhann *et al.*, 2011)

I. Core Clinical criteria

Dementia is diagnosed when there are cognitive or behavioral (neuropsychiatric) symptoms that:

- o Interfere with the ability to function at work or at usual activities; and
- Represent a decline from previous levels of functioning and performing; and
- Are not explained by delirium or major psychiatric disorder;
- Cognitive impairment is detected and diagnosed through a combination of (1) history-taking from the patients and knowledgeable information and (2) an objective cognitive assessment, either a "bedside" mental status examination or neuropsychological testing.
- The cognitive or behavioral impairment involves a minimum of two of the following domains:
 - Impaired ability to acquire and remember new information
 - Impaired reasoning and handling of complex tasks, poor judgement
 - Impaired visuospatial abilities
 - Impaired language functions
 - Changes in personality, behavior, or comportment
- II. Criteria for the clinical diagnosis of PROBABLE Alzheimer's disease Probable AD dementia is diagnosed when the patient:
 - o Meets criteria for dementia as described above and has the following characteristics:
 - Insidious onset;
 - Clear-cut history of worsening of cognition by report or observation; and
 - The initial and most prominent cognitive deficits are evident on history and examination in one of the following category.
 - Amnestic presentation
 - Nonamnestic presentations
- III. Other parameters increasing the certainty of AD dementia diagnosis
 - Evidence of causative mutation
 - Presence of AD biomarkers
 - Low CSF Aβ₄₂

0

- Positive PET amyloid imaging
- Elevated CSF tau (total tau and phosphorylated tau)
- Decreased fluorodeoxyglucose uptake on PET in temporo-parietal cortex
- Disproportionate atrophy on structural magnetic resonance imaging in medial, basal and lateral temporal lobe and medial parietal cortex.

## 2.0 Purpose

The statistical analysis plan (SAP) describes the statistical methods to be used during the reporting and analyses of data collected under AC Immune Protocol ACI-35-1802.

## 3.0 **Scope**

The SAP outlines the following:

- Study objectives
- Study design
- Variables analyzed and analysis sets
- Applicable study definitions
- Statistical methods

Any major updates to the SAP after finalization of the current version will be added to the SAP document history. If any non-administrative changes are required, the SAP will be updated by and approved again by the sponsor.

# 4.0 Introduction

This SAP should be read in conjunction with the study protocol and Case Report Form (CRF).

This version of the plan has been developed using the protocol(s) and CRF version specified in the title page.

Any further changes to the protocol and/or CRF may necessitate updates to the SAP.

# 5.0 Study Objectives

## 5.1 Primary Objective

The primary study objectives are to assess:

- The safety and tolerability of study vaccines
- The immunogenicity of study vaccines (induction of Immunoglobulin G [IgG] titers against phospho-Tau [pTau] in serum)

## 5.2 Secondary Objectives

The secondary study objectives are to further assess the immunogenicity of study vaccines including:

- To further assess the immunogenicity of study vaccines (induction of IgG titers against Tau and of Immunoglobulin M [IgM] titers against pTau and Tau in serum)
- To assess the avidity of antibodies elicited by immunization

## 5.3 Exploratory Objectives

- To explore the effect of study vaccines on putative biomarkers of the progression of AD, i.e. blood and/or Cerebrospinal Fluid (CSF) concentrations of total Tau and pTau proteins, Tau fragments and other related biomarkers
- To explore the effect of study vaccines on the activation of T-cells in blood
- To explore the activity of study vaccines on blood inflammatory cytokines (e.g., Interleukin-1B [IL-1β], IL-2, IL-6, IL-8, IL-10, Interferon-Gamma [IFN- γ], and Tumor Necrosis Factor alpha [TNF-α])

- To further explore the effect of study vaccines on the immune response (e.g. antibodies against vaccine components, functional capacity of vaccine-induced antibodies)
- To explore the effect of study vaccines on behavior, cognitive (including, in the Netherlands, the maintenance of the decisional capacity) and functional performance

# 6.0 Study Design

This section reflects the language from Global Protocol Version 7.0 dated 22-Oct-2021. Country-specific changes to the design of the study and the schedule of assessments have been included in the respective protocol versions (V7.0 dated 04-Nov-2021 (UK specific version)).

This is a multicenter prospective placebo-controlled, double-blind and randomized study to assess treatment with Tau targeted vaccines versus placebo over 50 weeks (i.e. 12 months) in up to 216 subjects with early Alzheimer's Disease. For both cohorts 1 and 2, immunizations will be performed at months 0 (Week 0), 2 (Week 8), 6 (Week 24)\* and 12 (Week 48). Based on the safety and immunogenicity results the protocol may be amended to test additional regimens. The subjects will be enrolled in up to 3 Cohorts, each with up to 72 subjects, the actual number depending on the number of sub-cohorts studied and the number of sub-cohorts in which expansion is performed.

\* Due to the Covid-19 pandemic, local travel restrictions in Finland effective as of 18 March 2020, and the need to preserve the safety of study participants, modifications were made to the schedule of immunizations of sub-cohort 1.1 subjects who had not received the 3rd injection at month 6 already: immunizations at month 6 (week 24) were not performed in 7 of 8 sub-cohort 1.1 subjects for whom the planned Visit 5 did not allow all assessments to be done according to the protocol. In addition, Visits 5 (Week 24), 6 (Week 26) and 7 (Week 36) were replaced by remote visits in case these fell during the at-risk period (refer to protocol sections 3.5.2. 10, 3.5.2.11, 3.5.2.12 and 3.5.2.14).

#### Cohort 1 with ACI-35.030

For all cohort 1 subjects, the treatment period will last 50 weeks with the treatment/placebo being administered 4 times as outlined in the previous paragraph. The treatment period is 50 weeks and will be followed by a 24-week safety follow-up period starting 2 weeks after the last administration. Subjects who for any reasons have received less than 4 administrations will be followed at least for the same duration after their last administration until week 74. The overall subject participation will be up to around 80 weeks from first screening (screening visit is estimated as 6 weeks; 50 weeks of treatment and 24 weeks of safety follow-up) to last safety follow-up visit.

In this cohort, the ACI-35.030 vaccine will be assessed. The placebo used will be a phosphatebuffered saline (PBS) solution. The administration route of treatment will be intramuscular. ACI-35.030 will be tested in up to 3 dose levels in cohort 1, within 3 sub-cohorts. Up to 32 subjects, depending on dose escalation and a decision to expand one sub-cohort, will be treated as outlined below.

#### Sub-cohort 1.1 (8 subjects)

ACI-35.030 at 300  $\mu$ g/dose will be administered in 6 subjects and the placebo will be administered in 2 subjects. The safety and tolerability data after all subjects have received the second injection in sub-cohort 1.1 permit dose escalation after review by Data Safety Monitoring Board (DSMB).

#### Sub-cohort 1.2 (8 subjects)

ACI-35.030 at 900 µg/dose will be administered in 6 subjects and the placebo will be administered in 2 subjects. The safety and tolerability data after all subjects have received the second injection in sub-cohort 1.2 permit dose escalation after review by DSMB.

#### Sub-cohort 1.3 (8 subjects)

ACI-35.030 at 1800  $\mu$ g/dose will be administered in 6 subjects and the placebo will be administered in 2 subjects.

#### Cohort 2 with ACI-35.054

All cohort 2 subjects will receive a second generation ACI-35 vaccine (JACI-35.054) administered alone. Administration schedule, route of administration, treatment duration and follow-up duration are identical to cohort 1. Up to 3 dose levels of JACI-35.054 administered by the intramuscular route will be tested in up to 3 sub-cohorts. The placebo used will be a phosphate-buffered saline (PBS) solution.

#### Sub-cohort 2.1 (8 subjects)

JACI-35.054 at 15 µg/dose will be administered in 6 subjects and the placebo will be administered in 2 subjects. The safety and tolerability data after all subjects have received the second injection in sub-cohort 2.1 permit dose escalation after review by DSMB.

#### Sub-cohort 2.2 (8 subjects) – Optional

JACI-35.054 at up to 60  $\mu$ g/dose will be administered in 6 subjects and the placebo will be administered in 2 subjects. This sub-cohort will be optional and may be conducted based on good safety and tolerability observed in sub-cohort 2.1 and in case the antibody response in this previous sub-cohort is anticipated to be optimized at the dosage of up to 60  $\mu$ g. At the time of the release of protocol version 7.0 dated 22 Oct 2021, this sub-cohort with a dosage of 60  $\mu$ g/dose has been initiated following the dose escalation after the 15  $\mu$ g/dose sub-cohort.

#### Sub-cohort 2.3 (8 subjects) – Optional

JACI-35.054 at up to 150  $\mu$ g/dose will be administered in 6 subjects and the placebo will be administered in 2 subjects. This sub-cohort will be optional and may be conducted based on good safety and tolerability observed in sub-cohort 2.2 and in case the antibody response in this previous sub-cohort is anticipated to be further optimized at a higher dosage.

#### Cohort 3 with ACI-35.030 and JACI-35.054 in sequential administration

The administration schedule, route of administration, duration of treatment and follow-up are identical to cohorts 1 and 2 but both vaccines ACI-35.030 and JACI-35.054 will be administered in a sequence based on non-human primate immunogenicity data and on data reviewed during the previous subcohort interim analyses (IA). In any of the sub-cohorts listed below, the selected dosages of the 2 study vaccines will have been evaluated in cohorts 1 and 2 and safety monitored for at least 10 weeks and safety data of the selected dosages of the 2 study vaccines reviewed by the DSMB.

**Note:** Planned as optional in the protocol, Sub-cohort 2.3 and all Cohort 3 have not been initiated since the data obtained during the study from other sub-cohorts was considered to be sufficient to inform the subsequent clinical development steps. Therefore, no analyses will be conducted.

#### Sub-cohort expansion

Optional sub-cohort expansion of up to 16 additional subjects (i.e. up to 12 on active treatment and up to 4 on placebo per sub-cohort) may be considered in sub-cohort(s) with a favorable safety and immunogenicity profile with the objective to confirm the initial sub-cohort(s) immunogenicity results. The number of additional subjects to be enrolled will be determined based on the observed immunogenicity response rate in the sub-cohort(s) and on the potential gain in precision of the response rate estimate in the expanded sub-cohort(s), and will not exceed 16 (i.e., up to 24 subjects overall per sub-cohort). In addition, all other immunogenicity endpoints available at the interim timepoint may be considered. The dose-level, sequence of administration and administration regimen of study vaccine(s) will be identical to the initial part of the sub-cohort.

**Note:** An expansion of 17 additional subjects was done in sub-cohort 1.2 (for a total of 25 subjects in that sub-cohort) to allow further assessment of safety and immunogenicity at that dose. It was considered that the recruitment of 17 (instead of up to 16 as planned per protocol) subjects is acceptable by the Sponsor.

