5.3.1 Sample Size Justification

Antibody titer assessment: The preliminary assessment of the antibody response and of the safety/tolerability (comparison between sub-cohorts) will be performed based on the data of all randomized subjects (6 on ACI-35.030/JACI-35.054 and 2 on placebo per sub-cohort) based on the timepoints related to the different IAs that will be conducted during the study. The initial number of subjects in each sub-cohort is consistent with the customary sample size employed in this type of studies. It is expected to allow clinical judgement of safety and tolerability, and to get preliminary evidence of an acceptable immune response. This sample size is also anticipated to provide sufficient evidence to support the possible enrollment of up to 16 additional subjects in the sub-cohort(s) showing the most favorable antibody response profile(s) with the objective to confirm the initial results. The number of additional subjects to be enrolled will be determined based on the preliminary observed immunogenicity response rate in the sub-cohort(s) and on the potential gain in precision of the response rate estimate in the expanded sub-cohort(s), and will not exceed 16 (12 on ACI-35.030/JACI-35.054 and 4 on placebo per sub-cohort). In addition, all other immunogenicity endpoints available at the interim timepoint may be considered in the sample size re-estimation. This may include but is not limited to the observed variability of titers such as the Anti-pTau IgG and the Anti-e-PHF IgG.

In total, up to 24 subjects can be randomized to cohort 1, cohort 2 and cohort 3, respectively (not taking into account sub-cohort(s) expansion). Any randomized subject withdrawing before the 2nd injection for reasons other than safety may be replaced in the cohort.

For safety, if an AE occurs at the rate of 1% or 10%, then the chance of observing such an AE among 6 subjects receiving that dose of active treatment will be 6% or 47%, respectively. If no AE of a given type is observed in any of the 6 subjects at a given dose of active treatment, then with 80% (90%) confidence the true incidence of that type of AE at that dose is at most 24% (32%). An optional recruitment expansion of up to 16 additional subjects may be considered in any sub-cohort to allow further assessment of safety at that dose.

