#### Rationale and Scope of IAs

The objectives of the above mentioned IAs in the sub-cohorts (whether expanded or not) is to ensure a regular review of safety, tolerability and immunogenicity with the support of optional biomarker data. A decision to escalate to the next dose in one given sub-cohort may be taken once IA data of the previous dose are available from Visit 4 (Week 10) onwards and pending prior DSMB approval. A decision to expand a sub-cohort may be taken based on satisfactory review of safety data by the DSMB and analysis of immunogenicity IA data of this sub-cohort dose from Visit 4 (Week 10) onwards. The IA at the end of the optional extended post-injection period is intended to monitor the durability of the immune response and any biomarker changes in blood.

In case data cut points occur within a short interval of time, interim analysis may be combined as deemed appropriate.

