# 11.0 Statistical Methods

All analyses will use SAS® version 9.4 or higher. Descriptive summaries will be tabulated by treatment group (ACI 300µg, ACI 900µg, ACI 1800µg, JACI 15µg, JACI 60µg). Where applicable, all subjects from each main cohort will be summarized together (excluding immunogenicity and biomarker TFLs).

Categorical data will be presented using counts and percentages, with the number of subjects in each category as the denominator for percentages. Percentages will be rounded to one decimal place except 100% will be displayed without any decimal places and percentages will not be displayed for zero counts.

Continuous data will be summarized using the number of observations (n), mean, standard deviation (SD), median, first quartile, third quartile, minimum, and maximum. Minimum and maximum will be rounded to the precision of the original data. Mean and median will be rounded to 1 decimal place greater than the precision of the original data. The SD will be rounded to 2 decimal places greater than the precision of the original data, up to a maximum of 3 decimal places.

A sensitivity analysis may be carried out at the end of the study if the number of patients impacted by the COVID-19 pandemic is large (e.g. >10% missed injections due to COVID-19) and thought to be impacting the efficacy and safety endpoints. This sensitivity analysis may exclude the patients affected by the pandemic.

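### The 900 µg expansion was meant to confirm a favourable early antibody response, but as the SAP reads the final tables give no estimate from the expansion subjects alone

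*SAP*

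**What the plan says.** Three elements of the plan bear on this.

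- **Who is expanded, and why.** SAP 6.0, under Sub-cohort expansion, gives the aim: a sub-cohort may be enlarged "with the objective to confirm the initial sub-cohort(s) immunogenicity results". Protocol 5.3.1, repeated in SAP 6.1, reserves expansion for the "sub-cohort(s) showing the most favorable antibody response profile(s) with the objective to confirm the initial results". Under Rationale and Scope of IAs, the SAP bases the decision on satisfactory DSMB safety review and "analysis of immunogenicity IA data of this sub-cohort dose from Visit 4 (Week 10) onwards". Other immunogenicity endpoints may also count. No numeric criterion is given.
- **What happened.** At 900 µg the vaccine "will be administered in 6 subjects and the placebo will be administered in 2 subjects" in the initial part. The SAP's note under Sub-cohort expansion reports 17 further subjects, 25 in all, and describes their purpose as learning more about safety and immunogenicity at that dose. It does not give their active/placebo split.
- **How results are shown.** SAP 11.0: "Descriptive summaries will be tabulated by treatment group", with one group for each of ACI 300, 900 and 1800 µg and JACI 15 and 60 µg. SAP 9.2 presents the ITT population by randomized arm. In Appendix 2, no final table, figure or listing title distinguishes initial from expansion subjects. Section 12.0, on changes from the protocol analysis, does not mention the matter.

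Appendix 3 lists interim looks for the Sub-cohort 1.2 Extension at Weeks 10, 26, 50 and 74. SAP 11.6.1 plans no tests of antibody responses.

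**The concern.** When a dose is enlarged because its first few subjects responded well, those subjects' results include some favourable chance. New subjects at the same dose do not share it. Confirmation in the ordinary sense asks whether the new subjects show what the first ones showed. A single 900 µg group cannot answer that, because about a third of its active subjects are those whose results prompted the expansion.

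The stake is interpretation. The protocol intends these endpoints to guide the choice of dose and vaccine for later development, and response rates are to be plotted against dose. An upward shift at one dose would enter that comparison unlabelled.

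**Working it through.** **1. The plan's own figures.** SAP 6.1 and Protocol 5.3.1 give probabilities only for adverse events among 6 active subjects. They reproduce:
- 1 − 0.99^6 = 5.9% (stated 6%); 1 − 0.90^6 = 46.9% (stated 47%).
- 1 − 0.20^(1/6) = 23.5% (stated 24%); 1 − 0.10^(1/6) = 31.9% (stated 32%).

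The plan gives no figure for what the expansion achieves.

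**2. Inputs.**
- From the documents: 6 initial active subjects; 17 added in total.
- Assumed: 12 added active subjects. The planned 3:1 ratio gives 17 × 0.75 = 12.75, so 12 or 13.
- Assumed, because the documents are silent: true response rate p, the form of the trigger, and that the reported visit is the one used to decide.

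**3. Formula.** Let X be the responders among the initial 6 and S the event that the dose is expanded.

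Pooled bias = [E(X | S) + 12p] / 18 − p

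This is 6/18 = 0.333 of the initial-part bias (6/19 = 0.316 with 13 added). The expansion-only bias is zero, because those subjects played no part in S.

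**4. Two examples.**
- Best of three equal doses, p = 0.70: E(X | S) = 5.10. Then (5.10 + 8.40)/18 = 0.750, a bias of +5.0 points.
- Trigger of at least 5/6, p = 0.50: E(X | S) = (5 × 6 + 6 × 1)/7 = 5.143. Then (5.143 + 6)/18 = 0.619, a bias of +11.9 points.

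**5. Range (bias of the pooled rate, percentage points, 6 + 12 active).**

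| True rate | Best of 2 | Best of 3 | At least 4/6 | At least 5/6 | 6/6 |
|---|---|---|---|---|---|
| 50% | 3.8 | 5.6 | 7.6 | 11.9 | 16.7 |
| 70% | 3.4 | 5.0 | 2.9 | 6.0 | 10.0 |
| 80% | 2.9 | 4.2 | 1.2 | 3.3 | 6.7 |
| 90% | 2.0 | 2.8 | 0.2 | 1.1 | 3.3 |
| 95% | 1.3 | 1.6 | 0.0 | 0.3 | 1.7 |

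At 40% the best-of-2 and best-of-3 values are 3.7 and 5.6. With 13 added active subjects every entry is equal or slightly smaller. At a true rate of 100% the bias is zero.

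**6. Titers.** Choosing the best of two or three equal doses shifts the pooled mean log titer by 0.077 or 0.115 SD. For an assumed log10 SD of 0.3 to 0.7, the geometric mean is too high by a factor of 10^(0.077 × 0.3) = 1.055 up to 10^(0.115 × 0.7) = 1.20.

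**7. Price of using the expansion alone.** The standard error ratio is √(18/12) = 1.22. As an illustration, the exact 95% interval is 51.6-97.9% for 10/12 and 58.6-96.4% for 15/18. On root mean squared error (RMSE), best of three at p = 0.70:
- Pooled: √(5.0² + 9.7²) = 10.9 points.
- Expansion-only: √(0.7 × 0.3/12) = 13.2 points.

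Pooling loses only under a strict trigger with a lower true rate. For at least 5/6 at 50%, the pooled RMSE is 15.4 points against 14.4.

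**The case against.** **Pooling is inferred.** No sentence says the two parts are combined. The group list in SAP 11.0 omits placebo, so it is not a full column layout, and the table shells are in a separate document. This stands. The point is about what the SAP shows, and if the shells already split the group, saying so in the SAP would close it.

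**The extension has its own interim looks.** They cover both primary antibodies and might supply the unselected estimate. But the SAP does not say that their outputs show extension subjects alone. They are recoded outputs for the sponsor's review committee. On Appendix 3's numbering they are Cohort 1 looks 8 to 11, whereas Appendix 2's interim column stops at Cohort 1 IA7. They do not put an expansion-only estimate in the final tables. Final subject listings might let a reader rebuild one, but that is not a planned result.

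**The size rests on an assumed rule.** This stands. A reader might infer that 900 µg was picked as the best of three doses. The documents do not say that it ranked first, or that all three doses had been read when it was expanded. They allow more than one sub-cohort to be expanded, each judged partly on safety.

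**The deciding visit may differ from the reported one.** This also stands. Expansion may be decided from Week 10, while Protocol 5.3.6.2 names Week 50 for the geometric mean and change from baseline. With best of three and an assumed Week 10 to Week 50 correlation of 0.3-0.7, the Week 50 bias falls to 0.9-2.4 points at a true rate of 70% and 0.4-1.1 at 90%.

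**The expansion was sized for precision.** The number added was to depend on how far it would sharpen the response-rate estimate of the enlarged sub-cohort, so pooling was evidently intended. This is a good reason to keep the pooled result. It does not make that result an independent confirmation.

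**Conclusion.** The concern holds as a gap in presentation. The expansion depends on the outcome and its stated aim is confirmation, yet the SAP as written plans no final estimate from the expansion subjects alone. Under any trigger that rises with the observed response, the pooled 900 µg estimate is biased upward in expectation, unless essentially everyone responds.

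The size cannot be determined from the documents. With 6 + 12 active subjects, one visit for selection and reporting, and best of two or three equal doses, it is about 3 to 6 points at true rates of 40-80% and 1 to 3 points at 90-95%. A fixed trigger of at least 5/6 gives 11.9 points at 50%, 3.3 at 80% and 0.3 at 95%. The bias is smaller at visits only weakly correlated with the deciding one.

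A reader might infer two stronger things. One is that the 900 µg result is materially inflated; neither the trigger nor the true rate is given, so this is not shown. The other is that the expansion-only estimate should replace the pooled one. In most of these scenarios the pooled estimate has the smaller overall error, so the choice is a trade-off. No error rate is affected, because the immunogenicity analysis is descriptive.

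**What to change.** In the final anti-pTau IgG and anti-ePHF IgG tables (14.2.1.x and 14.2.5.x) and the response-rate plots (Figures 14.1.1.3 and 14.1.5.3), keep the pooled 900 µg group and add initial-part and expansion-only results beside it. State that only the expansion-only result is independent of the data that triggered the expansion, and that the pooled result is more precise but carries some selection bias. One sentence naming the visit and endpoints that drove the decision would let readers judge how far the bias reaches other visits.

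The cost is a few extra columns and no new data. The expansion-only figures will be less precise, with a standard error about 1.2 times the pooled one.
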